[figure not shown]
[figure not shown]
[figure not shown]

CLINICAL TRIAL PROTOCOL

Document Number:		c02286986-03
BI Trial No.:	1321.6	
BI Investigational Products:	Idarucizumab	
Title:	Open label Phase I trial in healthy Chinese male and female volunteers to investigate pharmacokinetics and pharmacodynamics of idarucizumab to reverse dabigatran anticoagulant activity	
Lay Title:	Study to evaluate the safety, pharmacokinetics and pharmacodynamics of idarucizumab (BI 655075) administered alone or with dabigatran etexilate in Chinese healthy subjects	
Clinical Phase:	I	
Trial Clinical Monitor:	 Phone:  Fax: 	
Principal Investigator :	 Phone:  Fax: 	
Status:	Final Protocol (Revised protocol (based on global amendment 1))	
Version and Date:	Version: 2.0	Date: 17 Mar 2017
Page 1 of 98		
<small>Proprietary confidential information. © 2017 Boehringer Ingelheim International GmbH or one or more of its affiliated companies. All rights reserved. This document may not - in full or in part - be passed on, reproduced, published or otherwise used without prior written permission</small>		

CLINICAL TRIAL PROTOCOL SYNOPSIS

Name of company:		Boehringer Ingelheim	
Name of finished product:		Not Applicable	
Name of active ingredient:		Idarucizumab	
Protocol date: 20 Oct 2016	Trial number: 1321.6		Revision date: 17 Mar 2017
Title of trial:	Open label Phase I trial in healthy Chinese male and female volunteers to investigate pharmacokinetics and pharmacodynamics of idarucizumab to reverse dabigatran anticoagulant activity		
Principal Investigator:			
Trial sites:	Single centre [REDACTED]		
Clinical phase:	I		
Objectives:	To investigate pharmacokinetic and pharmacodynamic of idarucizumab administered at or close to the steady state of dabigatran		
Methodology:	Open label, single centre		
No. of patients:	12		
total entered:	12		
each treatment:	12 subjects (approximately sex ratio: 1:1)		
Diagnosis :	Not Applicable		
Main criteria for inclusion:	age \geq 18 and \leq 45 years, Body weight \geq 50 kg , BMI range: \geq 19 and $<$ 24 kg/m ²		
Test products:	a) Idarucizumab (50 mg/mL in buffer solution for infusion) b) Dabigatran etexilate (110 mg capsules); only as NIMP		
dose:	a) 2 short infusions of 2500 mg each 15minutes apart administered at or close to the steady state of dabigatran; b) 220 mg b.i.d		

Name of company:	Boehringer Ingelheim	
Name of finished product:	Not Applicable	
Name of active ingredient:	Idarucizumab	
Protocol date: 20 Oct 2016	Trial number: 1321.6	Revision date: 17 Mar 2017
mode of administration:	a) Intravenous infusion b) Oral	
Comparator products:	Not applicable	
dose:	Not applicable	
mode of administration:	Not applicable	
Duration of treatment:	a) 1 day (2 short infusions of 2500 mg each 15 minutes apart) b) 3 days twice daily (b.i.d.) with a single dose on day 4 (2 times at intervals of 3 days)	
Endpoints	The following pharmacokinetic (PK) parameters will be determined as primary endpoints; For idarucizumab: C_{max} , $AUC_{0-\infty}$, Ae_{0-72} The following pharmacodynamic (PD) parameters will be determined as primary endpoints; For dTT: $AUEC_{above, 2-12}$ on day 4 and day 11 The following pharmacokinetic (PK) parameters will be determined as secondary endpoints; For sum dabigatran: $Ae_{0-74,ss}$ on day 4 and day 11 For unbound sum dabigatran: AUC on day 4 and day 11 [REDACTED]	
Safety criteria:	Adverse events, laboratory tests (including haematology, clinical chemistry, urinalysis, coagulation parameters and ADA), vital signs (BP, PR, body temperature), 12-lead ECG, and local tolerability.	
Statistical methods:	Descriptive statistics for safety, PD and PK endpoints will be calculated.	

FLOW CHART 1

Treatment period		Trial Period		Visit	Day	Informed consent	In-/Exclusion Criteria	Dabigatran Administration	Administration of idarucizumab	Vital signs	12-lead ECG	pO2-monitoring	Laboratory / Urinalysis	Physical examination	Blood sampling for PD ⁷	Blood sampling for PK of Dabigatran ⁷	Blood sampling for PK of idarucizumab ⁷	Urine Collection for PK	Pregnancy Testing ⁹	ADA ⁸	Hospitalization	Adverse events / Concomitant med.
Treatment period	Scr.	1	-28 to -2	X		X				X ¹	X		X ^{2,3}	X ⁵								
			-1							X	X		X ³	X	X							
		1		X	X					X	X			X	X	X		X			X	
		2			X					X	X											
		3			X					X	X											
		4			X					X	X		X	X	X	X		X				
		5								X	X		X	X	X	X		X				
		6								X	X											
		7								X	X											
		8		X						X	X		X	X								
		9		X						X	X											
		10		X						X	X											
		11		X	X	X	X ¹	X	X	X	X	X ⁶	X	X	X	X	X					
		12								X	X		X ³	X	X	X	X	X				
		13								X	X		X ^{3,4}	X	X	X	X	X				
		14								X	X		X ³	X ⁶	X	X	X	X				
EOT	3	16 to 24								X	X		X ³	X ⁶				X	X			
FU1	4	39 to 45																			X	
FU2	5	102 to 108																		X		

1. Body temperature inclusive
2. Protein electrophoresis, lipase, amylase, hormone, drug and virus screening only at screen
3. Urinalysis including α 1-microglobulin, albumin and IgG
4. Urinalysis only
5. At the screening including subject information, demographics, relevant medical history, concomitant medication
6. Local tolerability inclusive.
7. PK and PD sampling times may be adapted based on information obtained during trial conduct
8. ADA (anti-idarucizumab Antibodies) samples will be taken at baseline, EOT, FU1 and FU2.
9. Urine pregnancy test required for all women of child bearing potential. Pregnancy testing is one indicator of pregnancy. Changes in a subject's menstrual cycle, that may indicate pregnancy must also be considered and a further pregnancy test can be taken if the Investigator feels it to be appropriate.

FLOW CHART 2

Part 1: Planned timetable for Treatment period (2 short infusions 15 minutes apart administered at or close to the steady state of dabigatran)

Visit	Day	Planned Time ¹ [h:min]	Actual daytime [h:min]	Dabigatran administration	Administration of idarucizumab	Vital signs	12-lead ECG	pO2 -monitoring	Laboratory / Urinalysis	Physical examination	Blood sampling for PD ^{4,5}	Blood sampling for PK of Dabigatran	Blood sampling for PK of idarucizumab ⁵	Urine Collection for PK [*]	Pregnancy Testing	ADA ⁶	Adverse events / Concomitant med.
2	-1					X	X		X ³	X	X						
	1	0:00	7:00	X		X ²	X ²			X ²	X ²	X ²		X ²		X ²	
		12:00	19:00	X													
	2	24:00	7:00	X		X ²											
		36:00	19:00	X													
	3	48:00	7:00	X		X ²	X ²										
		60:00	19:00	X													
	4	72:00	7:00	X		X ²	X ²		X ²	X ²	X ²	X ²					
		73:00	8:00								X	X					
		74:00	9:00								X	X					
	5	74:30	9:30								X	X					
		75:00	10:00								X	X					
	6	76:00	11:00								X	X					
		78:00	13:00								X	X					
	7	80:00	15:00								X	X					
		82:00	17:00														
	8	84:00	19:00								X	X					
		86:00	21:00														
	9	90:00	1:00								X	X					
		98:00	9:00			X					X	X	X				
	10	122:00	9:00			X					X	X					
		146:00	9:00			X	X				X	X					
	11	168:00	7:00	X		X ²	X ²		X ²	X ²							
		180:00	19:00	X													
	12	192:00	7:00	X		X ²											
		204:00	19:00	X													
	13	216:00	7:00	X		X ²	X ²										
		228:00	19:00	X													

*: Urine sampling for PK relative to morning administration: pre-dose on Day 1, 0–2 h, 2–6 h, 6–12 h, 12–14 h, 14–26 h, 26–50 h, 50–74 h on Day 4-7

FLOW CHART 2

Part 2: Planned timetable for Treatment and End of Study period (2 short infusions 15 minutes apart administered at or close to the steady state of dabigatran)

Visit	Day	Planned Time ¹ h:min]	Actual daytime [h:min]	Dabigatran administration	Administration of idarucizumab	Vital signs	12-lead ECG	pO2 -monitoring	Laboratory / Urinalysis	Physical examination	Blood sampling for PD ⁴ ⁵	Blood sampling for PK of Dabigatran ³	Blood sampling for PK of idarucizumab ⁵	Urine Collection for PK ^{**}	Pregnancy Testing	ADA ⁶	Adverse events / Concomitant med.	
2	11	240:00	7:00	X					X ^{2,3}	X	X ²	X ²	X ²					
		241:00	8:00								X	X						
		241:55	8:55		X-	X ^{2,7}	X ²	X ²		X ²	X ²	X ²	X ²					
		242:00	9:00		-X	X	X	X			X	X	X					
		242:05	9:05			X	X	X			X	X	X					
		242:15	9:15		X-	X ^{2,7}	X ²	X ²	X ^{3,8}	X ²	X ²	X ²	X ²					
		242:20	9:20			X	X	X			X	X	X					
		242:22	9:22										X					
		242:30	9:30			X	X	X					X					
		242:50	9:50			X	X	X					X					
		243:20	10:20			X'	X	X			X	X	X	X				
		244:00	11:00			X'	X	X	X ^{3,8}	X	X	X	X					
		245:00	12:00			X	X						X					
		246:00	13:00			X'	X		X ³	X	X	X	X					
		248:00	15:00			X	X				X	X	X					
		250:00	17:00															
		252:00	19:00								X	X	X					
		254:00	21:00			X ⁷	X		X ^{3,8}		X	X	X					
12		266:00	9:00			X	X		X ³	X	X	X	X					
		290:00	9:00			X	X		X ^{3,8}	X	X	X	X					
		314:00	9:00			X	X		X ³	X ⁹	X	X	X					
3	16 to 24					X	X		X ³	X ⁹					X	X		

**:Urine sampling on Day 11 relative to the end of the first idarucizumab infusion: -2 h-(5) min, -5 min-4 h, 4-10 h, 10-12 h, 12-24 h, 24-48 h, 48-72 h on Day 11-14

1. On the first dabigatran administration basis
2. Predose
3. Urinalysis including α 1 microglobulin, albumin and IgG
4. PD includes for each sampling point: Hemoclot® (dTT), aPTT, TT and ECT
5. PK and PD sampling times may be adapted based on information obtained during trial conduct.
6. ADA (anti-idarucizumab Antibodies) samples will be taken at baseline, EOT, FU1 and FU2 after idarucizumab administration.
7. Body temperature inclusive
8. Urinalysis only
9. Local tolerability inclusive.

TABLE OF CONTENTS

CLINICAL TRIAL PROTOCOL	1
CLINICAL TRIAL PROTOCOL SYNOPSIS	2
FLOW CHART 1	4
FLOW CHART 2	5
TABLE OF CONTENTS	7
ABBREVIATIONS	11
1. INTRODUCTION	14
1.1 MEDICAL BACKGROUND	14
1.2 DRUG PROFILE	16
2. RATIONALE, OBJECTIVES, AND BENEFIT - RISK ASSESSMENT	25
2.1 RATIONALE FOR PERFORMING THE TRIAL	25
2.2 TRIAL OBJECTIVES	25
2.3 BENEFIT - RISK ASSESSMENT	26
3. DESCRIPTION OF DESIGN AND TRIAL POPULATION	29
3.1 OVERALL TRIAL DESIGN AND PLAN	29
3.1.1 Administrative structure of the trial	29
3.2 DISCUSSION OF TRIAL DESIGN, INCLUDING THE CHOICE OF CONTROL GROUP	30

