3. DESCRIPTION OF DESIGN AND TRIAL POPULATION

3.1 OVERALL TRIAL DESIGN AND PLAN

This trial will be open label with only 1 dose group.

A total of 12 subjects will participate in the trial.

This trial consists of two periods; the dabigatran etexilate administration alone period is intended to evaluate the safety of multiple doses of 220 mg dabigatran etexilate b.i.d, and in the second period idarucizumab will be administered at or close to steady state of dabigatran and is intended for exploratory PK/PD analysis with the dose (2500 mg followed by 2500 mg).

At the dabigatran etexilate administration alone period, all subjects will receive 220 mg dabigatran etexilate b.i.d. (440 mg daily dose) for 3 days and a single 220 mg dose on day 4 to reach dabigatran or close to steady state.

Following dabigatran etexilate administration alone, after a washout period of 3 days and evaluation of safety 220 mg dabigatran etexilate will be administered twice daily over 3 days (from day 8 to day 10) with a single 220 mg dose on day 11. The dose of idarucizumab (2500 mg followed by 2500 mg is planned) will be administered intravenously approximately 2 hours after the last dabigatran administration.

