5.1.2 Secondary Endpoints

The following pharmacokinetic parameters will be determined as secondary endpoints, if feasible:

For sum dabigatran: $Ae_{0-74,ss}$ on day 4 and day 11

For unbound sum dabigatran: $AUC_{2-12,ss}$ on day 4 and day 11

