5.4.2.2 Urine sampling for pharmacokinetic analysis

Quantification of idarucizumab and dabigatran (unconjugated and sum dabigatran)

A blank urine sample will be collected prior to drug administration on day 1 and four aliquots of 2 mL each retained to check for analytical interference.

All urine voided during the sampling intervals listed in the [Flow Chart](#) will be collected in polyethylene (PE) containers and stored refrigerated (4-8°C) during the collection interval. Subjects have to empty their bladder at the end of each sampling interval. The consumption of water (100 mL) some time before the end of a planned urine fraction will support a timed urine collection. Therefore, subjects will be advised to drink at least 100 mL before the end of urine sampling interval. The urine weight/volume (weight will be set equal to volume, i.e. 1 kg = 1 L, without correction for specific gravity of urine) for each collection interval will be documented and four aliquots of 2 mL (idarucizumab and dabigatran analysis, except for urine samples obtained on day 4 to 7 (only two aliquots needed, as these samples will only be analysed for dabigatran analytes) each will be stored in polypropylene tubes for bioanalytical measurement at about -70°C or below.

Make sure that the urine voided within one collection interval is well mixed before preparing the aliquots. In case more than one collection container was used during a collection interval, the volume of all containers has to be mixed before aliquots are prepared. Mixing should be done by transferring the entire volume of all collection containers for a collection interval into a single PE/PP or glass container, and stirring the mixed fractions for about 1 minute

(manually or using a stir bar etc., device should be either PE/PP/Teflon or glass). The sample tube labels should list at least the following information: trial number, subject number, visit, planned time (interval start - stop), analyte (idarucizumab or dabigatran), matrix (urine) and aliquot number.

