5.6 OTHER ASSESSMENTS

A total amount of about 84 mL blood will plan to be taken per subject during the whole course of the trial for pharmacodynamic parameters (see [Flow Chart](#) for time points of blood sampling). With the exception of the primary endpoints dTT, all pharmacodynamic parameters are considered exploratory and analytical methods have been validated to fulfill the requirements of the exploratory analyses, 'fit-for-purpose' validation.

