7.7 DETERMINATION OF SAMPLE SIZE

It is planned to include a total of 12 subjects in this trial. The planned sample size is not based on a power calculation. A group size between 8 and 12 per dose level is commonly used in

healthy subject trials and is considered sufficient for exploratory investigation of single/multiple dose safety and pharmacokinetics.

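### Flow Chart 1 omits the PD, dabigatran PK and urine sampling on Days 6 and 7 that Flow Chart 2, Section 5.4.2.2 and the secondary endpoint Ae0-74,ss require

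*Protocol*

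**What the plan says.** Section 5.1.2 of the protocol sets a secondary endpoint: "For sum dabigatran: $Ae_{0-74,ss}$ on day 4 and day 11". The Day 4 value is the dabigatran-alone reference and the Day 11 value is the one with idarucizumab.

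Flow Chart 2, Part 1 times everything from the first dabigatran dose at 07:00 on Day 1. It has PD and dabigatran PK marks at 98:00, 122:00 and 146:00. Its urine footnote lists seven intervals after the Day 4 dose, the last four being "12–14 h, 14–26 h, 26–50 h, 50–74 h on Day 4-7". Section 5.4.2.2 likewise treats the Day 4 collection as lasting until Day 7, in its aliquot rule: "except for urine samples obtained on day 4 to 7".

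Flow Chart 1 has a column headed "Urine Collection for PK". It marks urine, PD and dabigatran PK on Days 4 and 5, and again on Days 11 to 14. On Days 6 and 7 it marks only vital signs and ECG.

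Section 5.6 gives the PD blood volume: "A total amount of about 84 mL blood will plan to be taken per subject". Section 6.2.2 refers staff to the flow chart for the time points of all procedures without saying which of the two it means.

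**The concern.** The two charts give different instructions for the same two days. Chart style does not explain the blanks, because Flow Chart 1 does mark PD, PK and urine on Days 12, 13 and 14, the corresponding days after the Day 11 dose.

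What is at stake is the comparability of the two periods. Ae0-74,ss on Day 4 needs urine up to 74 h after the dose, which falls on Day 7. If Day 4 urine ended early while Day 11 urine was complete, the dabigatran-alone reference would be too low or could not be calculated. An early end would also affect only one side of the comparison behind the Section 2.2 objective on idarucizumab's effect on dabigatran. With 12 subjects and a single uninterrupted stay, missed urine cannot be recovered. The PD and dabigatran PK samples on Days 6 and 7 are exposed to the same risk.

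**Working it through.** **1. Which days the Flow Chart 2 rows fall on.** The printed day labels in Part 1 are displaced in the extracted text, so I used the clock. Time 0:00 is Day 1, 07:00, and the Day 4 morning dose is at 72:00.

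- 98:00 + 7 h = 105 h = 4 full days + 9 h: Day 5, 09:00, 26 h after the dose.
- 122:00 + 7 h = 129 h = 5 full days + 9 h: Day 6, 09:00, 50 h after the dose.
- 146:00 + 7 h = 153 h = 6 full days + 9 h: Day 7, 09:00, 74 h after the dose.

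The urine intervals (0-2, 2-6, 6-12, 12-14, 14-26, 26-50, 50-74 h) have no gaps and end at 72 + 74 = 146 h. The last urine fraction therefore ends at the same time as the last PD and PK sample. After the Day 11 dose at 240:00, urine runs to 72 h after the end of the first infusion at 242:00. That is 314:00, again 74 h after the dose. The two collections are designed to match.

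**2. Which chart the blood volumes support.**

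- PD draws marked in Flow Chart 2: Day -1 (1), Day 1 (1), Day 4 (10), 98:00/122:00/146:00 (3), Day 11 (13), Days 12-14 (3). The total is 31.
- At 2.7 mL per draw (Section 5.6.2): 31 x 2.7 = 83.7 mL, which reproduces the stated figure of about 84 mL.
- Without Days 6 and 7: 29 x 2.7 = 78.3 mL, which does not.

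The PK volume in Section 5.4.2.1 (about 156 mL) points the same way but less sharply. There are 30 dabigatran draws of 4 mL. The extracted chart shows 19 idarucizumab draws of 2 mL, or 18 if the mark at 240:00 is not counted.

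- With Days 6 and 7: 120 + 36 = 156 mL (18 draws) or 120 + 38 = 158 mL (19 draws).
- Without them: 112 + 36 = 148 mL or 112 + 38 = 150 mL.

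The match is exact only with 18 draws, but either count favours including Days 6 and 7.

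**3. How much urine could be lost (illustration).** The terminal half-life of 12 to 17 h is from Section 1.2. The model is an assumption: one compartment, first-order absorption at 0.5 to 1 per h, and seven equal doses 12 h apart, with urinary excretion proportional to elimination. For one dose, the fraction eliminated by time t is

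F(t) = 1 - [ka·exp(-ke·t) - ke·exp(-ka·t)] / (ka - ke), with ke = ln 2 / half-life.

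A(s) is the sum over the seven doses of the amount eliminated between 0 and s hours after the Day 4 dose. The lost share is 1 - A(s)/A(74).

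| Collection stops at | Half-life 12 h | Half-life 17 h |
|---|---|---|
| 26 h (last interval ending on Day 5) | 22-23% | 32% |
| 41 h (midnight at the end of Day 5) | 8-9% | 15% |
| 50 h (the interval begun on Day 5 is completed) | 4-5% | 9% |

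The ranges within cells reflect the absorption rate. As a hand check, simple mono-exponential decay gives a lost share of (2^(-s/T) - 2^(-74/T)) / (1 - 2^(-74/T)). At s = 26 h this is (0.223 - 0.014)/0.986 = 21% for T = 12 h and (0.346 - 0.049)/0.951 = 31% for T = 17 h. A multi-phase profile with more early excretion would lose less.

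**4. Day 5.** As extracted, the Flow Chart 1 row has seven marks: vital signs, ECG, laboratory, physical examination, PD, dabigatran PK and urine. The 98:00 row of Flow Chart 2 has four. By position these are vital signs, PD, dabigatran PK and idarucizumab PK. The last cannot be meant before Day 11, so the row is damaged and cannot be read cell by cell.

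**The case against.** The strongest reply is that the protocol already prevents truncation. Flow Chart 1 carries no clock times and no urine intervals, so nobody could run the urine collection from it alone. The only intervals listed for Day 4 are those under Flow Chart 2, Section 5.4.2.2 repeats Day 4 to Day 7, and the endpoint name itself says 74 h. The trial has one site. This largely stands: it turns a predicted loss into a risk. It does not remove the contradiction, because no text gives either chart precedence. Amendment 1 also changed other cells expressly to keep the two charts consistent, so the sponsor evidently treats such mismatches as worth correcting.

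A reader might also infer that the Day 11 to Day 4 ratio of urinary dabigatran would be inflated about 1.3- to 1.5-fold. The documents do not support that as an expected result. It needs collection to stop at exactly 26 h, although Flow Chart 1 marks urine on Day 5, when the 26-50 h interval begins. It also needs an incomplete collection to be reported as Ae0-74, whereas Section 5.1.2 makes the parameter conditional on feasibility and Section 7.5.3 has parameters that cannot be determined flagged as not calculated. No such ratio of Ae is planned in the visible text.

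A further inference would be that Flow Chart 2 drops the safety checks between the two courses, although Section 3.1 says that "after a washout period of 3 days and evaluation of safety 220 mg dabigatran etexilate will be administered twice daily". This does not hold either. Vital signs remain at 98:00, and the row "146:00 9:00 X X X X" includes vital signs and ECG. Laboratory, ECG, physical examination and vital signs are all marked before the dose at 168:00 (Day 8). An evaluation of safety before the second course is therefore scheduled under either chart.

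**Conclusion.** The point holds as an internal inconsistency confined mainly to Days 6 and 7. Flow Chart 1 is wrong as written for PD, dabigatran PK and urine. Flow Chart 2, Section 5.4.2.2, the endpoint definition and the PD blood volume all agree against it, and this does not depend on the displaced day labels.

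The consequence is a possible loss of part of the Day 4 reference for one secondary endpoint, with no matching loss on Day 11. The plausible size depends on when collection would stop: about 4-9% of Ae0-74 at 50 h, 8-15% at 41 h and 22-32% at 26 h. These figures rest on the assumed one-compartment model and the protocol's half-life range. They illustrate the risk and do not forecast what would happen.

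The Day 5 difference is only apparent. The extracted 98:00 row is too damaged to show which assessments are missing, so the original chart has to be consulted before anything is concluded. The sample size is unaffected: "The planned sample size is not based on a power calculation".

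**What to change.** Add the PD, dabigatran PK and urine marks on Days 6 and 7 to Flow Chart 1, so that it matches Flow Chart 2 and Section 5.4.2.2. One sentence stating which chart governs timing would guard against any remaining mismatch.

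Separately, compare the Day 5 row of Flow Chart 1 with the 98:00 row of Flow Chart 2 in the original charts, and reconcile them for laboratory, ECG and physical examination. Which safety assessments belong there is for the sponsor to decide.

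The cost is a wording correction to the protocol. It adds no subjects, and the stated PD and PK blood volumes already include the Day 6 and 7 samples.

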During this trial, totally 5000 mg idarucizumab administered at or close to the steady state of dabigatran are planned. The dabigatran etexilate dosing schedule of 220 mg b.i.d. for 3 days + 1 dose on day 4 in healthy subjects is selected to achieve steady-state plasma concentrations similar to those observed in the patient population dosed with 150 mg b.i.d. in RE-LY ([Section 4.1.4](#)) ([U10-2017-01](#)). In Japanese healthy volunteers, the safety of dabigatran etexilate was confirmed with 300 mg for single dose administration and twice daily 150 mg for multiple dose administration ([U06-3091](#), [U06-3420](#), [U05-3334](#)). In Caucasian healthy volunteers, the safety was investigated with 600 mg for single dose administration and 400 mg up to 3 times daily for multiple dose administration. Safety and tolerability were confirmed up to 200 mg t.i.d. (600 mg as a daily dose) ([U99-1502](#), [U00-1856](#), [U06-1614-01](#), [U06-1609-01](#)). Additionally, the safety was confirmed with twice daily 225 mg multiple dose administration in patients undergoing an orthopaedic surgery ([U04-1195-01](#)). And twice-daily 300 mg multiple-dose administration was tried in patients with atrial fibrillation ([U06-1615-02](#)). Even though the risk of bleeding might be increased at a dose of 220 mg twice daily (440 mg as a daily dose) to Chinese healthy volunteers, the possibility of occurrence of severe adverse events is estimated very low. In this trial, the dabigatran etexilate administration alone period is intended to evaluate the tolerability and safety of multiple doses of 220 mg dabigatran etexilate. Subjects safety will be ensured by thorough monitoring including blood coagulation parameters under controlled environments. During in house confinement the subjects will be under medical observation and thoroughly monitored for any adverse events.

Especially, to minimize the risk of bleeding coagulation parameters will be closely monitored in subjects of the trial. Bleeding will be managed with the help of rescue medication, emergency procedures, and additional treatments regarding bleeding events ([Section 4.2.1](#)). Administration of trial drug will be immediately stopped in case of any clinically relevant adverse events or reactions. A clinical monitoring up to 24 hours after drug administration will be frequently performed (e.g. vital signs including body temperature, ECG, pO₂ monitoring, laboratory tests, local tolerability, and adverse events).

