5.3.5 Other safety parameters

PO2 monitoring

The PO2 monitoring will be evaluated by the investigator and any clinically relevant findings will be reported as an AE in eCRF. The results will not form part of the report, although the results are filed at the investigator's site as source documents.

Local tolerability

Local tolerability (for the time points see [Flow Chart](#)) will be assessed by the investigator or designee according to "swelling", "induration", "heat", "redness", "pain", or other findings. Findings during the trial should be documented as adverse events.

Anti-drug antibody (ADA)

Anti-drug antibody (ADA) will be collected at baseline, EOT, FU1 and FU2.

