7.8.5 Others

A frequency table will be provided for local tolerability.

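### Flow Chart 2 has no local-tolerability check before about 72 h after the infusions, in conflict with Flow Chart 1 and Protocol Section 2.3

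*Protocol*

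**What the plan says.** The Protocol synopsis lists local tolerability among the safety criteria. Section 5.3.5 makes it a structured assessment by the investigator or a designee, covering swelling, induration, heat, redness, pain and other findings. It refers to the Flow Chart for the time points without saying which of the two charts is meant. It adds: "Findings during the trial should be documented as adverse events".

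Three places bear on the timing:

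- **Flow Chart 2 Part 2** gives clock times. Its footnote reads "9. Local tolerability inclusive" and is attached to the physical examinations at 314:00 (Day 14) and at EOT (Day 16 to 24).
- **Flow Chart 1** gives days only. Its footnote reads "6. Local tolerability inclusive" and appears on the Day 11, Day 14 and EOT rows.
- **Section 2.3** says: "A clinical monitoring up to 24 hours after drug administration will be frequently performed". The examples that follow include "laboratory tests, local tolerability, and adverse events".

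SAP Section 7.8.5 plans the analysis in one sentence: "A frequency table will be provided for local tolerability". It names no time points.

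**The concern.** Flow Chart 1 and Section 2.3 both point to a local-tolerability check on or close to the infusion day. The timed schedule that staff would work from on Day 11 has none until about three days later. The documents do not say which source takes precedence.

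What is at stake is the content of the SAP 7.8.5 table. If the site follows Flow Chart 2, the structured items are first scored on Day 14, and anything that came and went earlier is absent from the scheduled assessments. A table without findings could then be read as covering the infusion day when it does not. This matters somewhat beyond the trial itself, because Section 2.2 plans to compare safety between Chinese, Japanese and Caucasian volunteers.

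**Working it through.** The plan gives no figure to reproduce, so the check is clock arithmetic and a comparison of passages.

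**Inputs.** From Flow Chart 2 Part 2, the first infusion ends at 242:00 and the second starts at 242:15. Table 4.1.4: 1 gives 5 minutes per infusion, so the second ends at 242:15 + 0:05 = 242:20. The examination times and their footnotes are from Flow Chart 2 Part 2.

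**Formula.** Elapsed time = planned time of the examination minus end of infusion.

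| Physical examination | After end of infusion 1 (242:00) | After end of infusion 2 (242:20) | Footnote 9 |
|---|---|---|---|
| 242:15 | 15 min | before infusion 2 | no |
| 244:00 | 2 h | 1 h 40 min | no |
| 246:00 | 4 h | 3 h 40 min | no |
| 266:00 (Day 12) | 24 h | 23 h 40 min | no |
| 290:00 (Day 13) | 48 h | 47 h 40 min | no |
| 314:00 (Day 14) | 72 h | 71 h 40 min | yes |
| EOT | Day 16 to 24 minus Day 11 = 5 to 13 days | same | yes |

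Of the six examinations after the second infusion, two carry the footnote: the last in-house one and EOT.

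**The sources side by side.**

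| Source | Earliest local-tolerability check |
|---|---|
| Flow Chart 2 Part 2 | 314:00, about 72 h after the infusions |
| Flow Chart 1 | Day 11, no clock time, before or after infusion not stated |
| Section 2.3 | within the monitoring up to 24 h, no clock time |
| Section 5.3.5 | defers to the Flow Chart, not specified which |

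The Day 11 mark in Flow Chart 1 does not settle the matter. Flow Chart 2 also has Day 11 physical examinations before the first infusion, at 240:00 and 241:55, so the mark could be satisfied without any post-infusion check.

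**How far the extracted table can be trusted.** Superscripts in Flow Chart 2 are degraded in places. The vital-signs cells at 243:20, 244:00 and 246:00 show a stray apostrophe where a footnote number probably stood. A damaged superscript therefore still leaves a trace. The physical-examination cells at 244:00 and 246:00 show a plain mark, which is reasonable evidence that no footnote is there. In Flow Chart 1 the Day 11 cells are shifted. The footnote is clearly on that row, but its place in the physical-examination column is inferred from the Day 14 and EOT rows.

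**The case against.** A reader might infer that the trial cannot describe acute infusion-site reactions at all. The documents do not support that. Subjects stay on site for at least 72 h after idarucizumab (Section 6.2.2) and are under medical observation (Section 2.3). Physical examination includes skin and extremities (Section 5.3.1) and is scheduled at about 2, 4, 24 and 48 h. Local findings are to be recorded as adverse events (Section 5.3.5), and all adverse events are collected from consent to follow-up visit 1 (Section 5.3.6.2). No passage limits detection to what a subject volunteers.

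Nor can it be said that no check at all is planned within 24 h. That holds only if Flow Chart 2 alone governs, and Flow Chart 1 does mark Day 11. Section 2.3 gives local tolerability as an example and commits to no clock times. The idea that local reactions peak in the first hours is clinically plausible but comes from no passage. The only local-tolerance data in the Protocol (Section 1.2) show no formulation-related injection-site effect in monkeys and no hemolysis of human blood. No primary or secondary endpoint is affected, and all analyses are descriptive.

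These points limit the concern but do not remove it. Adverse-event capture is not the same as a scheduled assessment. Under Section 5.3.1, only significant examination findings that meet the adverse-event definition must enter the eCRF, so the five local items are not required at 2, 4, 24 or 48 h. The SAP tabulates local tolerability separately from adverse events, and a frequency table needs scheduled assessments with a known denominator.

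**Conclusion.** The finding is an inconsistency between passages with a practical consequence. Flow Chart 2 first schedules local tolerability about 72 h after the infusions. Flow Chart 1 marks the infusion day, and Section 2.3 includes the check in monitoring up to 24 h. If the site follows Flow Chart 2, the SAP 7.8.5 table rests on two assessments per subject (12 × 2 = 24 in all), on Day 14 and at EOT, and earlier reactions appear only if recorded as adverse events.

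This rests on two assumptions: that the extracted charts show the footnotes correctly, and that staff work from the timed chart on Day 11. The first is reasonable but should be checked against the original pages. The second is not stated in the Protocol. It is worth correcting because the remedy costs little; it does not threaten the PK/PD objective.

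**What to change.** Reconcile Flow Chart 1, Flow Chart 2, Section 2.3 and Section 5.3.5:

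1. In Flow Chart 2 Part 2, add footnote 9 to the post-infusion physical examinations already scheduled on Day 11, at 244:00 and 246:00. Keep 314:00 and EOT.
2. If 266:00 is also marked, to cover the 24 h point in Section 2.3, add footnote 6 to Day 12 in Flow Chart 1. Marking 266:00 alone would create a new mismatch, because Day 12 has no such footnote there.
3. State in Section 5.3.5 which chart gives the local-tolerability time points.
4. In SAP Section 7.8.5, present the frequency table by time point, so that Day 11, Day 14 and EOT are not pooled.

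Cost: 12 subjects × 2 examinations = 24 added checks, or 12 × 3 = 36 with 266:00, at an estimated minute each, plus a few CRF fields. No visit or sample is added. Global amendment 1 (Section 11) already edited flow-chart entries to bring the two charts into line, so this is a change of the same kind.
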